Relationship and sexual satisfaction of stoma patients

18.04.2022

NCT ID: konstanz_001

Study protocol

Relationship and sexual satisfaction of stoma patients – study protocol

18.04.2022

Version 2

Head of study: Dr. med. [name]

deputy: [name]. med. [name]

Table of contents

1. Background	3
2. Aim	3
3. Participants	3
4. Methods	3
5. Statistics	3
6. Protection of data privacy	3
7. Risks	3
8. References	3

1 **Background**

Sexual dysfunctions are common after stoma operations with rectal cancer.¹ Sexual dysfunctions after rectum operations are a known complication.² Patients with stoma have a significantly lower self-esteem compared to healthy people.³ There is no research regarding the connection of a stoma and sexual satisfaction to the best of our knowledge. To advise patients before such an operation it is necessary to investigate such a connection.

2 **Aim**

- Sexual satisfaction of participants with stoma
- Relationship satisfaction of participants with stoma
- Comparing colostomy and ileostomy
- Sensitize people treating patients with stoma

3 **Patients**

Patients with stoma or after having had a stoma are asked to fill out an online questionnaire regarding sexual and relationship satisfaction.

Minimum age: 18 years

No sexual dysfunctions. No disease influencing sexual functioning

4 **Methods**

Anonymous Questionnaire. Retrospective data analysis.

5 **Statistics**

Empiric data analysis of answers and comparing answers to literature.

6 **Protection of data privacy**

Questionnaire is anonymous. Data is only available with password. Only head of study and deputy have access to data.

7 **Risks**

The study is an anonymous questionnaire. The data is analysed retrospectively. So there are no risks for participants.

8 **References**

1. Sutunbuloglu, E., & Vural, F. (2018). Evaluation of sexual satisfaction and function in patients following stoma surgery: A descriptive study. *Sexuality and Disability*, 36(4), 349-361.
2. Hendren, S. K., O'Connor, B. I., Liu, M., Asano, T., Cohen, Z., Swallow, C. J., ... & McLeod, R. S. (2005). Prevalence of male and female sexual dysfunction is high following surgery for rectal cancer. *Annals of surgery*, 242(2), 212.

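### Does the no-risk statement in Section 7 need changing because intimate answers are newly collected from participants?

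*Protocol*

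**What the plan says.** Section 7 is the protocol's only statement on risk. It gives two reasons and a conclusion: first the anonymity of the questionnaire, then "The data is analysed retrospectively. So there are no risks for participants".

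The other sections that bear on this are:

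- Section 3 (Patients), on where the data come from: "Patients with stoma or after having had a stoma are asked to fill out an online questionnaire regarding sexual and relationship satisfaction". The same section sets a minimum age and excludes people with sexual dysfunction or with a disease that affects sexual functioning.
- Section 4 (Methods), which is the whole description of the design: "Anonymous Questionnaire. Retrospective data analysis".
- Section 1 (Background), on the population: "Patients with stoma have a significantly lower self-esteem compared to healthy people". It also notes that sexual dysfunction is frequent after stoma surgery for rectal cancer.
- Section 6 (Protection of data privacy): "Questionnaire is anonymous. Data is only available with password. Only head of study and deputy have access to data".
- Section 5 (Statistics): "Empiric data analysis of answers and comparing answers to literature".

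**The concern.** A reader who meets the word retrospective expects existing records to be analysed, in which case nobody is approached and nobody is burdened. Section 3 describes something else: people are asked intimate questions for the purpose of this study, which most statisticians would call a cross-sectional survey. If the no-risk conclusion depends on the data already existing, it depends on something that Section 3 contradicts. The other reason, anonymity, protects against disclosure and not against the discomfort of answering. The Background adds weight, because it reports lower self-esteem in this population than in healthy people.

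Two things would be at stake. One is participant protection: a categorical denial of risk might explain why the protocol describes no measure against distress. The other is statistical: if people who find the items upsetting stop partway, and if they are the less satisfied ones, the remaining answers would overstate satisfaction.

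**Working it through.** The protocol gives no figure on this point, so there is nothing to reproduce. The check sets the sections side by side.

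**1. Is the retrospective label false?** There are two readings.

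- *Existing data are used.* Section 3 would contradict this. However, neither Section 4 nor Section 7 mentions records, charts or an existing data set.
- *Answers are analysed once they have been collected.* In both sections the word qualifies the analysis, and in Section 4 it comes directly after the questionnaire has been named as the source. On this reading Sections 3, 4 and 7 agree.

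The second reading fits the text at least as well. The term is imprecise, but a false statement is not shown.

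**2. Does the no-risk conclusion follow?** No, on either reading. Analysing answers after collection says nothing about the burden of giving them, and the measures in Section 6 concern confidentiality only. The conclusion is therefore stronger than its reasons. This part of the concern is correct.

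**3. Does the Background make distress foreseeable?** Only in part. The self-esteem sentence is a comparison with healthy people, and it is made for patients with a stoma. Section 3 also admits people who no longer have one, to whom that sentence is not explicitly applied. The remark on sexual dysfunction concerns a group that Section 3 largely excludes. Nothing in Section 1 concerns reactions to being questioned. Some discomfort is plausible, but that is an inference and not something the protocol reports.

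**4. Are safeguards absent?** This cannot be established. A protocol's risk section is not participant information. Neither the consent material nor the questionnaire is in the text, so it is unknown what participants are told, whether items may be left blank, or whether a contact is shown. The safeguards against disclosure are stated in Section 6.

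**5. Is there a bias?** Let *f* be the share of invited respondents whose answers are lost through break-off or skipping, *m_c* the mean score of those who answer and *m_l* the mean score of those lost. The mean over everyone is (1 − f)·m_c + f·m_l, so

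bias = m_c − [(1 − f)·m_c + f·m_l] = f·(m_c − m_l).

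The protocol gives neither *f* nor *m_c − m_l*. It does not even give the sign of the difference, which is what an upward bias would need. Rewording Section 7 or relabelling Section 4 alters neither term.

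**6. Would changing the questionnaire help?** An option to decline an item could turn some break-offs into single skipped items, which would reduce the loss. It could also turn some answers into skips, which would increase it. The net effect on *f* is unknown, and the protocol gives no basis for expecting a gain.

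**The case for a change.** The strongest argument for acting is that Section 7 is the only risk assessment in the document and draws an explicit conclusion that its two reasons do not support. Someone judging the study from the protocol would be given an absolute statement where minimal risk, with possible discomfort, would be the careful one. Correcting two sentences costs almost nothing, and the design would be named more accurately for later readers.

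What stands is the point about reasoning and tone: the absolute claim is overstated, and the design term invites misreading. What does not stand is the step from there to consequences. That participants are misinformed, that nothing is in place for those who feel uncomfortable, and that satisfaction will be overestimated are all assertions that the document neither supports nor contradicts. A low cost of rewording does not by itself justify a change when no result depends on it.

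**Conclusion.** No change to the plan is called for. The no-risk sentence does not strictly follow from its reasons, and the retrospective label is loose, but this is a matter of wording. Any reader of Section 3 can see that the answers are newly collected, and an analyst would treat the data as survey responses whatever the label. The effect on any estimate, comparison or conclusion is nil, and the suggested effect on missing answers cannot be given a size or a direction.

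This rests on two assumptions. The first is that retrospective means analysed after collection, which the text allows but does not spell out. The second is that what participants are told, and how items can be answered, is settled in the consent material and the questionnaire, which cannot be checked here. If the second assumption failed, the issue would be one of participant protection, and the descriptive analysis in Section 5 would still be unaffected.
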